## Appendix H Performance of droplet digital PCR (ddPCR) for MET amplification testing

Table A: The consistency of ddPCR and FISH in detecting MET amplification in tissue samples

FISH	ddPCR, n				Sensitivity	Specificity	Concordance	$\kappa$
	MET amp	Polysomy	MET neg	Total				
MET high amp	1	0	0	1				
MET low amp	8	0	0	8				
Polysomy	0	6	0	6				
MET neg	0	0	87	87				
Total	9	6	87	102				

*amp* amplification, *neg* negative

Table B: The concordance of MET amplification between tissue and matched peripheral blood samples detected by ddPCR

Tissue	Peripheral blood, n				Sensitivity	Specificity	Concordance	$\kappa$
	MET amp	Polysomy	MET neg	Total				
MET amp	4	0	5	9				
Polysomy	0	6	0	6				
MET neg	1	0	87	88				
Total	5	6	92	103				

*amp* amplification, *neg* negative

Table A: In tissue samples from 102 advanced NSCLC patients who had progressed on EGFR-TKI, the consistency of MET amplification between ddPCR testing and FISH testing. (1 case failed for FISH detection owing to the lack of sufficient tumor cells, remaining 102 cases had both FISH and ddPCR results) [26]

Table B: In tissue and the matched peripheral blood samples from 103 advanced NSCLC patients who had progressed on EGFR-TKI, the concordance of MET amplification detected by ddPCR between tissue and matched peripheral blood samples (In total, all 103 patients were involved in this analysis) [26].

EC	Ethics Committee, synonymous to Institutional Review Board (IRB) and Independent Ethics Committee (IEC)
ECOG	Eastern Cooperative Oncology Group
eCRF	electronic Case Report Form
EGFR	Epidermal Growth Factor Receptor
FAS	Full Analysis Set
FDA	Food and Drug Administration
FFPE	Formalin Fixed and Paraffin Embedded
FISH	Fluorescent in Situ Hybridization
GCP	Good Clinical Practice
HIV	Human Immunodeficiency Virus
HR	Hazard Ratio
IB	Investigator's Brochure
ICF	Informed Consent Form
ICH	International Council for Harmonisation
IEC	Independent Ethics Committee
IHC	Immunohistochemistry
IRB	Institutional Review Board
MRI	Magnetic Resonance Imaging
NE	Not Evaluable
NL	New Lesion
NSCLC	Non-Small Cell Lung Cancer
NTL	Non-Target Lesion
ORR	Objective Response Rate
OS	Overall Survival
PD	Progression of Disease
PET	Positron Emission Tomography
PFS	Progression-Free Survival
PR	Partial Response

Abbreviation or special term	Explanation
RECIST 1.1	Response Evaluation Criteria in Solid Tumors, Version 1.1
SAP	Statistical Analysis Plan
SD	Stable Disease
SoA	Schedule of Activities
TKI	Tyrosine Kinase Inhibitor
TL	Target Lesion
TOC	Table of Contents
WHO	World Health Organisation
ddPCR	Droplet Digital PCR

AMENDMENT HISTORY

Date	Brief description of change
16-11-2023	Initial version
17-05-2024	Updated to V2.0 with following changes: 1. Added overall percent agreement as a measurement of concordance of NGS in tissue and plasma for secondary endpoint analysis. 

1. OBJECTIVES

1.1 Objectives

This statistical analysis plan is for AstraZeneca "Gene Profile in EGFRm Locally Advanced or Metastatic NSCLC patients post Osimertinib 1L treatment failure: A real-world, multicenter Study (GPS)" (Study code: D5161R00037) and will give a detailed description of the planned analysis. This version of SAP is for interim analysis and final analysis. Tigemed is responsible for baseline characteristics, Geneplus is responsible for gene related analysis. **CC1**

CC1

This statistical analysis plan is based on the 2.0 version of the research protocol on January 20, 2023, the 3.0 version of the Case Report Form on Dec 27, 2023.

Objectives and Endpoints

[figure not shown]
Objectives	Endpoints
Primary	
● Gene profile in tissue Gene profile defined as gene alternation detected by NGS and frequency of every gene alternation. All gene alterations include gene mutation, copy number variation(CNV), fusion, etc. The frequency of all gene alteration detected by NGS(%) = (number of patients with every gene alteration detected by NGS)/(total number of patients in the FAS)×100%.
Secondary	
● Gene profile in plasma Gene profile defined as gene alternation detected by NGS and frequency of every gene alternation.● Concordance of plasma and tissue Using selected representative genes (for example EGFR, MET, PIK3CA and etc.) to measure the concordance Concordance of Gene X in plasma and tissue is defined as sensitivity, specificity, positive predictive value (PPV) and negative predictive value (NPV) between plasma and tissue results., Tissue sample is the reference standard.
- sensitivity=(number of patients with positive result in both plasma and tissue)/(total number of patients with positive result in tissue samples)×100%;- specificity=(number of patients with negative result in both plasma and tissue)/(total number of patients with negative result in tissue samples)×100%.- PPV (%)=(number of patients with positive result in both plasma and tissue)/(total number of patients with positive result in plasma samples)×100%;- NPV (%)=(number of patients with negative result in both plasma and tissue)/(total number of patients with negative result in plasma samples)×100%;● The percentage of pathology transformation

	Pathology transformation is defined as those transformation from non-small-cell lung cancer to small-cell lung cancer or from adenocarcinoma to squamous carcinoma, can be observed by IHC
CCI	CCI

2. STUDY DESIGN AND SAMPLE SIZE

2.1 Schema

Study Design A Real World, Multicenter Study

RECIST 1.1=Response Evaluation Criteria in Solid Tumors, Version 1.1.
NSCLC, non-small cell lung cancer; EGFR, epidermal growth factor receptor.

Figure 1 Study Design

2.2 Sample size

Approximately 200 participants in EGFRm locally advanced or metastatic NSCLC with the evidence of disease progression following 1L Osimertinib will be enrolled and 15 sites will be involved to elucidate the gene profile in paired tissue and plasma so that approximately 180 participants whom would be get gene profile, assuming a 10% drop-out.

Assuming some common gene alteration with an incidence of 20%, then with 200 subjects the 95% CI will be around 14.7% - 26.2% based on an exact method (Clopper-Pearson).

Table below summarizes the 95% CIs for the target incidences ranging from 10% to 50% with sample size of 200.

Assumed incidence of gene mutation	95% CI
10%	6.2%, 15.0%
20%	14.7%, 26.2%
30%	23.7%, 36.9%
40%	33.2%, 47.1%
50%	42.9%, 57.1%

In addition, 200 subjects are enough to have 86% probability to observe at least one case if the incidence of an gene alteration is 1%.

Note: "Enrolled" means a participant's, or their legally acceptable representative's, agreement to participate in a clinical study following completion of the informed consent process. Potential participants who are screened for the purpose of determining eligibility for the study, but are not randomly assigned/assigned in the study, are considered "screen failures", unless otherwise specified by the protocol.

Human Biological Sample Analysis:

Participants will be required to provide paired tissue and whole blood after disease progression following 1L Osimertinib. 200 tissue samples and 200 whole blood samples will be used to detect gene alteration by NGS, respectively. 200 tissue samples will be used to detect pathological transformation by IHC. Approximately 80-100 tissue samples will be used to test MET overexpression by MET IHC and MET amplification by FISH respectively. Approximately 80-100 whole blood samples will be used to test MET amplification by ddPCR.

3. ANALYSIS SETS

3.1 Definition of analysis sets

The following populations are defined:

Table 1 Populations for Analysis

Population/Analysis Set	Description
Enrolled	All participants who sign the ICF
FAS	All participants who meet the required inclusion/exclusion criteria and have valid Gene data from both plasma and tissue. CCI

3.2 Violations and Deviations

The list of protocol deviations will be finalized and documented before the database lock.

Protocol deviations will be collected, reviewed and reconciled throughout the study. Important protocol deviations (IPDs) will be identified from the complete set of protocol deviations. IPDs are those which may significantly impact the completeness, accuracy, and/or reliability of the study data or that may significantly affect a patient's rights, safety, or wellbeing.

A set of pre-determined IPDs are listed in the section 'Protocol Deviation Categories' in the protocol deviations tracking log.

The IPDs are grouped in to the following PD categories, where full details of the individual IPDs within each IPD category are provided in the protocol deviations plan:

- Informed consent problem.
- Inclusion/exclusion criteria.
- Lack of labs/other procedures.
- Visit schedule.
- Others

4. EXPOSURE(S) AND OUTCOMES

4.1 Exposures

Not applicable.

4.1.1 Definition of primary drug exposure

Not applicable.

4.1.2 Definition of comparison drug exposure

Not applicable.

4.2 Outcomes

4.2.1 Safety

Not applicable.

4.2.2 Primary outcome(s)

Gene profile in tissue

Gene profile is defined as gene alteration detected by NGS and frequency of every gene alteration. All gene alterations include gene mutation, copy number variation(CNV), fusion, etc.

4.2.3 Secondary outcome(s)

Gene profile in plasma

Gene profile is defined as gene alteration detected by NGS and frequency of every gene alteration.

[figure not shown]
Proportion of Gene X alteration(%) = (number of patients with Gene X alteration, which is an example of a certain gene)/(total number of patients in the FAS)×100%.

Concordance of plasma and tissue

Using selected representative genes (for example EGFR, MET, PIK3CA and etc.) to measure the concordance of plasma and tissue mutation for each gene. Concordance of Gene X in plasma and tissue is defined as sensitivity, specificity, positive predictive value (PPV) and negative predictive value (NPV) between plasma and tissue results.

The percentage of pathology transformation

Pathology transformation is defined as those transformation from non-small-cell lung cancer to small-cell lung cancer or from adenocarcinoma to squamous carcinoma, can be observed by IHC.

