Currently, analysis of circulating tumor DNA(ctDNA) has been the predominant method to investigate acquired resistance mechanisms, but non-genetic mechanisms of resistance, including histologic transformation and protein expression change cannot be captured by plasma NGS analysis. Compared to tissue analysis, sensitivity for copy number changes and chromosomal rearrangements using plasma samples is instable[3, 4, 19-23]. ddPCR is as technique with high sensitivity and specificity, which is widely used for the absolute quantification of nucleic acid through Poisson distribution [24] and also as an alternative technique for MET amplification testing in plasma samples has been explored in some previous studies. Kitazono et al. have attempted to use ddPCR to detect MET amplification in three blood samples of NSCLC patients with EGFR-TKI resistance and proved its feasibility at the first time [25]. The recent study further explored the performance of MET amplification testing by ddPCR in tissues and paired peripheral blood samples from advanced NSCLC patients who had progressed on EGFR-TKI[26]. A total of tissues and the paired peripheral blood samples from 103 advanced NSCLC patients who had progressed on EGFR-TKI were collected for MET amplification testing by using ddPCR. In parallel, MET amplification was verified by FISH in tissue samples. The concordance rate of MET amplification in tissue samples between ddPCR and FISH was 100% (102/102), and it was 94.17% (97/103) by ddPCR testing between tissue and paired and peripheral blood samples with performance of sensitivity 66.67% and specificity 98.86%. Therefore, ddPCR is an potentially alternative method for MET amplification testing in both tissues and peripheral blood samples, which is worthy of exploring and validating in more studies (appendix H).

Thus, this study plans to use paired tumor tissue and whole blood to detect molecular and histologic mechanisms of resistance to 1L Osimertinib and to assess the concordance of plasma and tissue. And these paired tissue and blood samples are also used to assess the concordance of MET amplification between FISH and ddPCR testing as exploratory endpoints. Additional, the prevalence of MET amplification by FISH testing and MET overexpression by IHC testing, and the overlap ratio of prevalence between MET amplification and MET overexpression are also as exploratory endpoints in this study.

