### 4.2 Scientific Rationale for Study Design

#### 4.2.1 Rationale for primary, secondary and exploratory endpoint

The primary objective is to describe the gene profile in tissue in *EGFR*m locally advanced or metastatic NSCLC patients post on 1L Osimertinib failure, which could help clinicians provide the following treatment strategy.

The secondary objective is to describe the gene profile in plasma, to assess the concordance of plasma and tissue, and the percentage of pathology transformation. Gene profile in plasma and the percentage of pathology transformation will be detected and analysed by NGS and IHC, respectively. Concordance of plasma and tissue is to explore whether plasma can be substitute for tissue when patients cannot accept tissue biopsy, which is defined as sensitivity, specificity, PPV and NPV of representative genes. According to the assay performance, sensitivity 80% is acceptable. If the point estimate for sensitivity is  $\geq 80\%$ , plasma samples are supposed to be consistent with tissue sample for NGS testing.

In the case of sufficient tissue samples, the exploratory endpoints is further to assess prevalence of MET amplification by FISH in tissue samples, the concordance of MET amplification

between FISH testing in tissue samples and ddPCR testing in blood samples, the prevalence of MET overexpression by MET IHC testing and the overlap ratio of prevalence between MET amplification by FISH and MET overexpression by MET IHC. The prevalence data of MET overexpression by MET IHC and MET amplification by FISH in post 1L Osimertinib resistance patients in China are very limited.

Tissue were unavailable for some patients post 1L Osimertinib and ddPCR testing will offer alternative method for MET amplification testing in blood samples. Concordance of MET amplification testing between ddPCR in plasma samples and FISH in tissue samples is to explore whether plasma can be substitute for tissue when patients cannot accept tissue biopsy, which is defined as sensitivity, specificity, PPV and NPV of representative genes.

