#### **4.2.2 Testing for common *EGFR* mutations**

Only participants with NSCLC with common *EGFR* mutations of ex19del and L858R will be eligible for inclusion in the study. A patient can be considered eligible for the study on the basis of documented *EGFR*m through any of ARMS, Super-ARMS, NGS analysis from accredited laboratories.

For patients eligible for inclusion in the study based on the pre-existing common *EGFR*m plasma and/or tissue sample results, the local *EGFR* tissue testing laboratory methods will be recorded in the respective electronic case report forms (eCRF).

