##### **8.3.2.2.2 Concordance of plasma and tissue**

Using selected representative genes (for example *EGFR*, MET, PIK3CA and etc.) to measure the concordance. Concordance of Gene X in plasma and tissue is defined as sensitivity,

[figure not shown]
specificity, positive predictive value (PPV) and negative predictive value (NPV) between plasma and tissue results. Tissue sample is the reference standard. The 95% confidence intervals using Pearson-Clopper method will be provided.

- sensitivity=(number of patients with positive result in both plasma and tissue)/(total number of patients with positive result in tissue samples)×100%;
- specificity=(number of patients with negative result in both plasma and tissue)/(total number of patients with negative result in tissue samples)×100%.
- PPV (%)=(number of patients with positive result in both plasma and tissue)/(total number of patients with positive result in plasma samples)×100%;
- NPV (%)=(number of patients with negative result in both plasma and tissue)/(total number of patients with negative result in plasma samples)×100%

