5.4.2 Secondary Endpoint

The secondary objective is to assess gene profile in plasma, concordance of plasma and tissue and the percentage of pathology transformation will be analysed by NGS method and IHC. All gene alterations in plasma(e.g., gene mutation, amplification, deletion, fusion, etc.) detected will be observed. Proportion of Gene X alteration(%) = (number of patients with Gene X alteration, which is an example of a certain gene)/(total number of patients in the FAS)×100%. Some cases which patients have more than one gene alteration need to be considered, therefore percentages may not add up to 100%.

Using selected representative genes to measure the concordance. The representative genes should include the top 20 mutated genes observed in tissue samples. Concordance of Gene X in plasma and tissue is defined as sensitivity, specificity, positive predictive value (PPV), negative predictive value (NPV), and overall percent agreement between plasma and tissue results., Tissue sample is the reference standard.

Sensitivity=(number of patients with positive result in both plasma and tissue)/(total number of patients with positive result in tissue samples)×100%;

Specificity=(number of patients with negative result in both plasma and tissue)/(total number of patients with negative result in tissue samples)×100%.

[figure not shown]
PPV (%)=(number of patients with positive result in both plasma and tissue)/(total number of patients with positive result in plasma samples)×100%;

NPV (%)=(number of patients with negative result in both plasma and tissue)/(total number of patients with negative result in plasma samples)×100%.

Overall percent agreement(%) =(number of patients with same result <positive or negative> in both plasma and tissue)/(total number of patients in FAS)×100%

Pathology transformation defines as pathological type of lung cancer change, which will be confirmed by pathologists. Number and percentage of patients with pathology transformation will be summarized. Proportion of pathology transformation(%) = (number of patients with pathology transformation)/(total number of patients in the FAS)×100%.

CCI

CCI

[REDACTED]

[REDACTED]
[REDACTED]
[REDACTED]

[REDACTED]

[figure not shown]
		[REDACTED] [REDACTED]	[REDACTED]	
[REDACTED]	[REDACTED]			
	[REDACTED]			
[REDACTED]				

[REDACTED]
[REDACTED]
[REDACTED]
[REDACTED]
[REDACTED]
[REDACTED]

[REDACTED]
[REDACTED]
[REDACTED]
[REDACTED]
[REDACTED]
[REDACTED]
[REDACTED]
[REDACTED]

CCI

CCI

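### Plasma–tissue concordance is defined per gene in patients all selected for EGFR ex19del/L858R, so the EGFR row, read as written, mainly measures founder detection and says little about C797X

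*SAP*

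**What the plan says.** Protocol 4.2.2 restricts entry to NSCLC whose common EGFR "mutations of ex19del and L858R will be eligible for inclusion in the study". Protocol 5.1, criterion 4, requires that mutation to be documented before first-line osimertinib.

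The concordance endpoint is then defined gene by gene. SAP 4.2.3 reads: "Using selected representative genes (for example EGFR, MET, PIK3CA and etc.) to measure the concordance of plasma and tissue mutation for each gene". Protocol 8.3.2.2.2 uses the same unit: "Concordance of Gene X in plasma and tissue is defined as sensitivity", followed by specificity, PPV and NPV. SAP 5.4.2 adds overall percent agreement, takes as the sensitivity numerator the "number of patients with positive result in both plasma and tissue", and sets the list of rows: "The representative genes should include the top 20 mutated genes observed in tissue samples". None of these sections defines a positive result for EGFR, treats the founder apart from other EGFR alterations, or asks for the same variant in both samples.

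Two other places bear on how the rows will be read. Protocol 2.2 says the paired samples are used "to detect molecular and histologic mechanisms of resistance to 1L Osimertinib and to assess the concordance of plasma and tissue". Protocol 4.2.1 asks whether plasma can stand in for tissue and gives a benchmark: "According to the assay performance, sensitivity 80% is acceptable". If the sensitivity point estimate reaches that level, "plasma samples are supposed to be consistent with tissue sample for NGS testing".

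**The concern.** EGFR is the gene on which patients were selected. At gene level, being EGFR-positive in tissue at progression is therefore close to a restatement of an entry criterion, and being EGFR-positive in plasma largely means that the founder was seen in plasma. A C797X call found in tissue and missed in plasma leaves the patient positive in both columns, and so concordant.

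The protocol's rationale names C797X (7%) and MET amplification (15%) as the most common acquired mechanisms after first-line osimertinib in the plasma study it cites. On-target EGFR resistance is thus one of the things a clinician would want to know whether plasma can show. A high EGFR sensitivity could be taken as reassurance on that question, and a low one as a warning, when it answers neither.

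**Working it through.** **Inputs**
- Evaluable pairs: 200 enrolled less 10% = 180 (SAP 2.2).
- C797X carriers: 0.07 × 180 = 12.6, about 13. The 7% comes from a plasma study (Protocol 1.1, Rationale) and is used here as a tissue prevalence, which is an assumption. A range of 4–10% gives 7–18 carriers.
- All 180 EGFR-positive in tissue, and every C797X carrier also carrying the founder: assumptions.
- Founder detection in plasma, *f*: not given in the documents; 70–90% assumed.
- Intervals: Clopper–Pearson, as in Protocol 8.3.2.2.2.

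**The plan's own figure.** The documents give no number for the EGFR row. The exact method reproduces the sample-size table: 40/200 gives 14.7–26.2%, as stated.

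**Gene-level EGFR sensitivity.** Let *c* = 13/180 and let *s* be the plasma sensitivity for C797X.

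1. If C797X is seen in plasma only when the founder is seen, sensitivity = *f* whatever *s* is. The shift is 0 points.
2. If the two are detected independently, sensitivity = *f* + *c*(1 − *f*)*s*. Moving *s* from 0 to 1 gives an expected shift of 13(1 − *f*)/180:
   - *f* = 70%: 3.9/180 = 2.2 points (70.0 to 72.2%)
   - *f* = 80%: 2.6/180 = 1.4 points (80.0 to 81.4%)
   - *f* = 90%: 1.3/180 = 0.7 points (90.0 to 90.7%)
3. Under any dependence, only the 13 carriers can change status, so the ceiling is 13/180 = 7.2 points.

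**Range.** Under independence, 7 carriers give 0.4–1.2 points and 18 carriers give 1.0–3.0 points. The ceilings are 7/180 = 3.9 and 18/180 = 10.0 points. If only 162 patients are EGFR-positive in tissue at progression, 13 carriers give 0.8–2.4 points, with a ceiling of 13/162 = 8.0.

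**Illustration.** At 85% founder detection the row is 153/180 = 85.0% (95% CI 78.9–89.9). In case 1 it reads the same whether plasma finds C797X in 0 of 13 carriers or in 11 of 13 (0.85 × 13 = 11.05).

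**What a separate row would show.** 0/13 gives 0–24.7%; 11/13 = 84.6% gives 54.6–98.1%. The intervals are wide, but these two outcomes are clearly distinguishable.

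**The case against.** The strongest reply is that the wording is loose, not wrong. Concordance of plasma and tissue mutation for each gene can be read as matching mutations within a gene, and the laboratory may do exactly that. This stands as far as it goes: a same-variant rule is not excluded. A reader might infer that the plan commits itself to counting a missed C797X as agreement. The documents do not go that far; they leave the point open. Redacted exploratory sections could also hold variant-level work, but the secondary-endpoint definition is itself visible and does not settle it.

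A second reply is that the EGFR row serves its stated purpose, since finding the known driver in plasma bears on whether plasma can replace tissue. That is fair, and it is a reason to report founder detection under its own name.

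Third, a reader might infer that the EGFR row decides the 80% question. The text does not support this. Protocol 4.2.1 speaks of representative genes in the plural, SAP 5.4.2 calls for at least 20 of them, and the SAP does not repeat the benchmark. The link is a risk of misreading.

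Fourth, alteration frequencies are reported separately in tissue and plasma (SAP 4.2.2 and 4.2.3), and SAP 5.4.1 adds an OncoPrint under the tissue endpoint. A gross plasma shortfall in C797X would show in the frequencies. They are marginal rates, however, and do not show which patients' tissue findings were missed in plasma.

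**Conclusion.** The concern holds for the EGFR row, on the visible text read as written. That row mainly measures plasma detection of the founder. The whole range of possible C797X performance moves it by 0 points if detection is nested, by an expected 0.7–2.2 points under independence at 70–90% founder detection, and by at most 7.2 points under any dependence. The middle figure is an expectation and not a bound. All three rest on 180 evaluable patients, all EGFR-positive in tissue, and 13 C797X carriers.

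The point does not extend to MET, PIK3CA or the other genes, on which patients were not selected; a reader who inferred that every row needs exact-variant scoring would be going beyond the problem. The primary endpoint and the sample-size figures are unaffected. In a descriptive study this is a correction to one secondary table, worth making because a more informative version is available from data already held.

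**What to change.** For the EGFR row only, in SAP 4.2.3 and 5.4.2 (recorded in the SAP's section on changes to protocol planned analyses) and in Protocol 8.3.2.2.2:

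1. Report plasma detection of each patient's documented founder ex19del or L858R separately, labelled as such.
2. Give EGFR alterations other than the founder, for example C797X, their own 2×2 table. Count a patient as concordant only if the same variant is called in both samples, show Clopper–Pearson intervals, and keep these rows descriptive.
3. In Protocol 4.2.1, state that the 80% plasma-consistent-with-tissue statement does not rest on the founder-driven gene-level EGFR row.

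Other genes can stay at gene level.

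The cost is wording and re-tabulation. The pipeline in Protocol Appendix F already produces variant-level calls, and SAP 4.3.1 already lists gene name and variant classification at diagnosis, so the founder can be identified per patient. No new samples are needed. The drawback is precision: with about 13 carriers, 11/13 spans 54.6–98.1%. A point-estimate threshold of 80% on that row would be unreliable: it needs at least 11 of 13, which a true sensitivity of 80% reaches with probability 0.50 and a true 90% with 0.87.
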